5.7. Discontinuation of Investigational Product and Withdrawal from Study

Individual subjects may be discontinued from IMPs in the following situations:

- Severe non-compliance to study protocol.

Individual subjects will be discontinued from IMPs in the following situations:

- Healthy subject decision. The healthy subject is at any time free to discontinue treatment, without prejudice to further treatment.
- Adverse events which in the opinion of the Investigator warrant discontinuation of the subject from treatment for his/her well-being, including (but not limited to):
 - A serious adverse reaction (ie, a SAE considered at least possibly related to IMP administration).
 - A severe non-serious adverse reaction (ie, a severe non-serious AE considered at least possibly related to IMP administration).
- Any significant and clinically relevant changes in the safety parameters (eg, ECG, BP, pulse, laboratory assessments, and AE) making the continuation of IMP administration unjustified, including:
 - Any case of Potential Hy's Law (PHL) or Hy's Law (HL) according to threshold values listed in [Appendix C](#).
 - QTc prolongation defined as QTcF > 500 ms, or a prolongation from baseline of > 60 ms, confirmed on a repeat 12-lead ECG.
 - Hypertension defined as an increase in resting supine systolic BP > 40 mmHg to above 180 mmHg and persisting for at least 10 minutes.
 - Tachycardia defined as resting supine heart rate > 125 bpm persisting for at least 10 minutes.
 - Symptomatic bradycardia defined as resting supine heart rate < 45 bpm or asymptomatic bradycardia defined as resting heart rate < 40 bpm while awake persisting for at least 10 minutes.
 - Severe hypokalaemia defined as serum potassium < 3.0 mmol/L (confirmed by repeat measurement).
- Any suspected or confirmed COVID-19 case in the judgment of the Investigator or Sponsor to protect the safety of the subject, other study participants or study site staff.

The appropriate AE form in the CRF must be completed.

5.7.1. Procedures for Withdrawal of a Subject from the Study

If a subject withdraws or is withdrawn from the study, the subject will be encouraged to continue with safety assessments in the respective treatment period and return to the Clinical Unit for an Early Termination Visit to ensure the subject's safety.

5.7.2. Procedures for Lost to Follow-up

A subject will be considered lost to follow-up if he or she repeatedly fails to return for scheduled visits and is unable to be contacted by the study site.

The following actions must be taken if a subject fails to return to the clinic for a required study visit:

- The site must attempt to contact the subject and reschedule the missed visit as soon as possible and counsel the subject on the importance of maintaining the assigned visit schedule and ascertain whether or not the subject wishes to and/or should continue in the study.
- Before a subject is deemed lost to follow-up, the Investigator or designee must make every effort to regain contact with the subject (where possible, 3 telephone calls and, if necessary, a certified letter to the subject's last known mailing address or local equivalent methods) until the end of study. These contact attempts should be documented in the subject's medical record.
- Should the subject continue to be unreachable, he or she will be considered to have withdrawn from the study. Site personnel, or an independent third party, will attempt to collect the vital status of the subject within legal and ethical boundaries for all subjects randomised, including those who did not get IMP.

5.8. Premature Termination of the Study

The study will be terminated prematurely if:

- The Investigator and the Sponsor assess that the number and/or severity of AEs justify discontinuation of the study in accordance with stopping rules listed in the Guideline on strategies to identify and mitigate risks for first-in-human and early clinical trials with investigational medicinal products (EMA/CHMP/SWP/28367/07 Rev.1), ie,:
 - A 'serious' adverse reaction (ie, an SAE considered at least possibly related to the IMP administration) in 1 subject.
 - 'Severe' non-serious adverse reactions (ie, severe non-serious AEs considered at least possibly related to the IMP administration) in 2 subjects, independent of within or not within the same SOC.
- The Sponsor considers the applied doses of the IMPs to be no longer relevant.
- The Sponsor decides to discontinue the study.

- New data become available and raise concern about the safety of IMPs so that continuation would pose potential risks to the subjects.
- New data become available regarding COVID-19, which raise concern for the safe study conduct so that continuation would pose potential risks to the subjects or the study site staff.

Premature termination of the study must be mutually agreed upon by the Investigator and the Sponsor and must be documented. However, study results will be reported according to the requirements outlined in this CSP as far as applicable.

6. COLLECTION OF STUDY VARIABLES

6.1. Recording of Data

Standard measures to assess PK, safety and tolerability apply during the study. For the single doses of IMPs planned to be given during this study, no safety issues are expected.

For timing of assessments refer to [Table 3](#).

6.2. Enrolment and Screening Procedures

Viral serology for assessment for hepatitis and HIV, and tests for use/abuse of drugs of abuse, alcohol, and smoking (cotinine) will be carried out, and subjects who have positive results for any of these will be excluded from the study. In addition, SARS-CoV-2 serology at screening and SARS-CoV-2 RT-PCR on admission will be assessed for eligibility. Follicle stimulating hormone (females only) and use of concomitant medication will also be assessed and reported.

Phone calls will be made 1 day prior to each respective visit to record signs and symptoms of COVID-19 or any contact with persons having confirmed SARS-CoV-2 infection. In case of signs or symptoms or contact, the visit will be cancelled and reason for cancellation will be appropriately documented.

6.3. Safety and Eligibility Measurements

Safety and tolerability variables will include:

- Adverse events
- Clinical laboratory assessments (haematology, clinical chemistry, and urinalysis).
- Physical examination
- 12-Lead ECGs
- Vital signs (systolic and diastolic BP, pulse, and tympanic temperature)

6.3.1. Adverse Events

6.3.1.1. Definition of Adverse Events

An AE is the development of any untoward medical occurrence in a subject or clinical study subject administered a medicinal product and which does not necessarily have a causal relationship with this treatment. An AE can therefore be any unfavourable and unintended sign (eg, an abnormal laboratory finding), symptom (for example nausea, chest pain), or disease temporally associated with the use of a medicinal product, whether or not considered related to the medicinal product.

The term AE is used to include both serious and non-serious AEs and can include a deterioration of a pre-existing medical occurrence. An AE may occur at any time, including washout period, even if no IMP has been administered.

6.3.1.2. Definitions of Serious Adverse Event

An SAE is an AE occurring during any study phase (ie, screening, treatment, washout, follow-up), that fulfils one or more of the following criteria:

- Results in death
- Is immediately life-threatening
- Requires in-patient hospitalisation or prolongation of existing hospitalisation
- Results in persistent or significant disability or incapacity or substantial disruption of the ability to conduct normal life functions
- Is a congenital abnormality or birth defect
- Is an important medical event that may jeopardise the subject or may require medical intervention to prevent one of the outcomes listed above

For further guidance on the definition of an SAE, see [Appendix A](#) of this CSP.

Adverse events for malignant tumours reported during a study should generally be assessed as SAEs. If no other seriousness criteria apply, the ‘Important Medical Event’ criterion should be used. In certain situations, however, medical judgment on an individual event basis should be applied to clarify that the malignant tumour event should be assessed and reported as a non-serious AE. For example, if the tumour is included as medical history and progression occurs during the study, but the progression does not change treatment and/or prognosis of the malignant tumour, the AE may not fulfil the attributes for being assessed as serious, although reporting of the progression of the malignant tumour as an AE is valid and should occur. Also, some types of malignant tumours, which do not spread remotely after a routine treatment that does not require hospitalisation, may be assessed as Non-Serious; examples include Stage 1 basal cell carcinoma and Stage 1A1 cervical cancer removed via cone biopsy.

6.3.1.3. Other Significant Adverse Events

During the evaluation of the AE data, an AstraZeneca medically qualified expert will review the list of AEs that were not reported as SAEs or where relevant AEs leading to discontinuation of IMP and withdrawal from the study. Based on the expert’s judgment, significant AEs of particular clinical importance may, after consultation with the Global Safety Physician, be considered OAEs and reported as such in the CSR. A similar review of other data from laboratory tests, vital signs, ECGs and other safety assessments will be performed for identification of OAEs.

Examples of these are marked haematological and other laboratory abnormalities, and certain events that lead to intervention (other than those already classified as serious), dose reduction or significant additional treatment.

6.3.1.4. Recording of Adverse Events

Time Period for Collection of Adverse Events

Non-serious AEs will be collected from administration of IMP in Treatment Period 1 throughout the treatment period and including the Follow-up Visit.

Serious AEs will be recorded from the time of informed consent.

Follow-up of Unresolved Adverse Events

Any AEs that are unresolved at the subject's last visit in the study are followed up by the Investigator for as long as medically indicated, but without further recording in ClinBase™.

AstraZeneca retains the right to request additional information for any subject with ongoing AE(s)/SAE(s) at the end of the study, if judged necessary.

Variables

The following variables will be collected for each AE:

- AE diagnosis/description.
- The date and time (if known) when the AE started and stopped.
- Maximum intensity.
- Whether the AE is serious or not.
- Investigator causality rating against the IMPs (yes or no).
- Action taken with regard to IMP.
- Outcome.

In addition, the following variables will be collected for SAEs:

- Date AE met criteria for SAE.
- Date Investigator became aware of SAE.
- AE is serious due to.
- Date of hospitalisation.
- Date of discharge.
- Probable cause of death.
- Date of death.

- Autopsy performed.
- Causality assessment in relation to study procedure(s).
- Causality assessment to other medication.

The following intensity ratings will be used:

- 1 Mild (awareness of sign or symptom, but easily tolerated).
- 2 Moderate (discomfort sufficient to cause interference with normal activities).
- 3 Severe (incapacitating, with inability to perform normal activities).

It is important to distinguish between serious and severe AEs:

- Severity is a measure of intensity whereas seriousness is defined by the criteria in Section 6.3.1.2.
- An AE of severe intensity need not necessarily be considered serious. For example, nausea that persists for several hours may be considered severe nausea, but not an SAE. On the other hand, a stroke that results in only a limited degree of disability may be considered a mild stroke but would be an SAE.

Causality Collection

The Investigator will assess causal relationship between IMPs and each AE, and answer “yes” or “no” to the question “Do you consider that there is a reasonable possibility that the event may have been caused by the IMP?”

For SAEs, causal relationship will also be assessed for other medication, any additional drug and study procedures. Note that for SAEs that could be associated with any study procedure the causal relationship is implied as “yes”.

A guide to the interpretation of the causality question is found in [Appendix A](#) of this CSP.

Adverse Events Based on Sign and Symptoms

All AEs spontaneously reported by the subject or reported in response to the open question from the study personnel: “Have you had any health problems since you were last asked?” or revealed by observation will be collected and recorded in ClinBase™.

When collecting AEs, the recording of diagnoses is preferred (when possible) to recording a list of signs and symptoms.

However, if a diagnosis is known and there are other signs or symptoms that are not generally part of the diagnosis, the diagnosis and each sign or symptom will be recorded separately.

Adverse Events Based on Examinations and Tests

The results from protocol-mandated laboratory tests, vital signs, ECGs and other safety assessments will be summarised in the CSR.

Deterioration as compared to baseline in protocol-mandated laboratory values, vital signs, ECGs and other safety assessments should therefore only be reported as AEs if they fulfil any of the SAE criteria or are the reason for discontinuation of treatment with the IMPs.

If deterioration in a laboratory value or vital sign is associated with clinical signs and symptoms, the sign or symptom will be reported as an AE and the associated laboratory result or vital sign will be considered as additional information.

Wherever possible the reporting Investigator should use the clinical, rather than the laboratory term (eg, anaemia versus low haemoglobin value).

In the absence of clinical signs or symptoms, clinically relevant deteriorations in non-protocol-mandated parameters should be reported as AE(s).

Any new or aggravated clinically relevant abnormal medical finding at a physical examination as compared with the baseline assessment will be reported as an AE.

Hy's Law

Cases where the subject shows elevations in liver biochemistry may require further evaluation and occurrences of AST or ALT $\geq 3 \times$ ULN together with total bilirubin $\geq 2 \times$ ULN may need to be reported as SAEs. Please refer to [Appendix C](#) for further instruction on cases of increases in liver biochemistry and evaluation of Hy's Law.

COVID-19

Adverse event questioning will include specific questions regarding signs and symptoms of COVID-19, including fever, dry cough, dyspnoea, sore throat, fatigue, and loss of taste or smell as well as potential recent (within previous 14 days) exposure to someone who has COVID-19 symptoms or positive test result.

Suspected and confirmed SARS-CoV-2 infection and COVID-19 will be recorded as AEs.

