3. STUDY DESIGN

3.1. Overall Study Design and Flow Chart

This study will be an open-label, randomised sequence, 2-period, 2-cohort, 2-treatment in each cohort, cross-over study in healthy subjects (males and females of non-childbearing potential), performed at a single study centre.

The study will comprise:

- A screening period of maximum 28 days;
- Two treatment periods:
 - Treatment Period 1 starts with admission to the Clinical Unit on Day -1, followed by dosing on Day 1 with the assigned treatment (A, B, C, or D) as per assigned cohort and treatment sequence, followed by a washout period of at least 14 days. Subjects will be discharged from the Clinical Unit after the last PK sample was collected for this treatment period (Day 4).
 - Treatment Period 2 starts with admission to Clinical Unit on Day -1, followed by dosing on Day 1 with cross-over treatment as per assigned cohort, followed by a follow-up period of 7 to 10 days. Subjects will be discharged from the Clinical Unit after the last PK sample was collected for this treatment period (Day 4).
- A follow-up visit/early termination visit at 7 to 10 days after the last IMP administration.

Subjects will be assigned to either Cohort 1 (tacrolimus) or to Cohort 2 (cyclosporin). Each cohort will have 2 treatment periods. Subjects in each cohort will be randomly assigned to one of 2 treatment sequences (AB|BA or CD|DC) where,

- Treatment A: Tacrolimus [CCI].
- Treatment B: Tacrolimus [CCI] + SZC [CCI].
- Treatment C: Cyclosporin [CCI].
- Treatment D: Cyclosporin [CCI] + SZC [CCI].

Subjects who have received Treatment A in Treatment Period 1 of Cohort 1 will receive Treatment B in Treatment Period 2 and vice versa. Subjects who have received Treatment C in Treatment Period 1 of Cohort 2 will receive Treatment D in Treatment Period 2 and vice versa.

Each subject will receive a single dose of oral capsules of tacrolimus [CCI]/cyclosporin [CCI] on 2 occasions, once alone and once in combination with oral suspension of SZC [CCI]. All drug administrations will occur after a 12 hour overnight fast.

Details on IMPs administration is provided in Section 5.4.3.

The Study Flow-Chart is presented in [Figure 3-1](#) and the Overall Graphical Representation of the study scheme is illustrated in [Figure 3-2](#).

The Schedule of Assessments displaying assessments/tasks and time points is presented in [Table 3](#).

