^c Residential periods start on Day -1 and end at 72 hours after dosing on Day 1 of each treatment period. Subjects should come to the Clinical Unit in the morning of Day -1 of each treatment period to have fasting safety laboratory samples collected and having results available in the afternoon to decide on the subject's eligibility/continuation.

^d Single doses of tacrolimus **CCI** or cyclosporin **CCI** will be administered per assigned cohort and treatment sequence on Day 1 of each treatment period, after an overnight fast of 12 hours.

^e For subjects assigned to BA or DC treatment sequence.

^f For subjects assigned to AB or CD treatment sequence.

^g Blood samples for tacrolimus/cyclosporin PK analysis to be collected at pre-dose, 0.25, 0.5, 0.75, 1, 1.25, 1.5, 1.75, 2, 2.25, 2.5, 3, 4, 6, 8, 10, 12, 16, 24, 36, 48, and 72 hours post-dose.

^h 12-Lead ECGs to be taken at pre-dose, 4, 24, 48, and 72 hours post-dose.

ⁱ Vitals signs (BP, pulse; supine) to be performed at pre-dose, 4, 24, 48, and 72 hours post-dose.

^j Clinical laboratory assessments and urinalysis to be performed 48 hours post-dose.

^k Blood samples for serum potassium levels to be taken at pre-dose and at 4, and 72 hours post-dose.

^l Tympanic temperature will be performed daily; pre-dose on Day 1.

^m Phone calls will be made 1 day prior to each respective visit to record signs and symptoms of COVID-19 or any contact with persons having confirmed SARS-CoV-2 infection. In case of signs or symptoms or contact, the visit will be cancelled and reason for cancellation will be appropriately documented.

ⁿ The result of the SARS-CoV-2 RT-PCR testing must be available prior to dosing on Day 1 of each treatment period.

Abbreviations: BP = blood pressure; COVID-19 = coronavirus disease 2019; ECG = electrocardiogram; FSH = follicle stimulating hormone; PK = pharmacokinetics; RT-PCR = reverse transcriptase polymerase chain reaction; SAE = serious adverse events; SARS-CoV-2 = severe acute respiratory syndrome coronavirus 2; SZC = sodium zirconium cyclosilicate.

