6.3.4. Resting 12-lead Electrocardiogram

At the time points specified in the SoA (Table 3), a 10-second 12-lead safety ECG, including QTcF, PR, QRS QT interval, and HR will be obtained after 10 minutes supine rest, using the site's own ECG machines.

The Investigator will judge the overall interpretation as normal or abnormal and this evaluation will be reported in ClinBase™. If abnormal, it will be further documented as to whether or not the abnormality is clinically significant by the Investigator. For all abnormalities (regardless of clinical significance) the specific type and nature of the abnormality will be documented in ClinBase™. Clinically significant findings should also be documented on the AE page of the CRF if applicable.

The Investigator may add extra 12-lead resting ECG safety assessments if there are any abnormal findings or if the Investigator considers it is required for any other safety reason. These assessments should be entered as an unscheduled assessment.

All subjects who have QTc prolongation defined as QTcF > 500 ms, or a prolongation from baseline of > 60 ms on repeat 12-lead ECG, should immediately have serum potassium assessed, if not already done within 1 hour of performing the ECG.

All ECG readings will be digitally stored as source documents.

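### A symptom-free, non-serious laboratory, vital-sign or ECG finding at a Section 5.7 discontinuation level is an AE after the Period 1 dose but not after the Period 2 dose

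*Protocol*

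**What the plan says.** Protocol Section 6.3.1.4, under the heading on examinations and tests, limits AE reporting for protocol-mandated assessments. Deteriorations from baseline should "only be reported as AEs if they fulfil any of the SAE criteria or are the reason for discontinuation of treatment with the IMPs". The reason given is that these results are summarised in the CSR anyway. The same section makes accompanying signs or symptoms AEs in their own right. It collects non-serious AEs from the Period 1 dose to the Follow-up Visit. Section 10.1.1 assigns events that start after the Period 2 dose to the Period 2 treatment.

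On dosing, Section 3.1 gives tacrolimus or cyclosporin "on 2 occasions, once alone and once in combination with oral suspension of SZC". The footnotes to Table 3 state that single doses "will be administered per assigned cohort and treatment sequence on Day 1 of each treatment period". Period 2 consists of admission, "followed by dosing on Day 1 with cross-over treatment as per assigned cohort, followed by a follow-up period of 7 to 10 days".

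Section 5.7 lists findings for which IMP will be discontinued. Two examples are "QTc prolongation defined as QTcF > 500 ms, or a prolongation from baseline of > 60 ms, confirmed on a repeat 12-lead ECG" and "Severe hypokalaemia defined as serum potassium < 3.0 mmol/L (confirmed by repeat measurement".

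Two other places bear on the rule. Section 6.3.4 says of ECGs: "Clinically significant findings should also be documented on the AE page of the CRF if applicable". Section 6.3.1.1 defines an AE broadly, as possibly "any unfavourable and unintended sign (eg, an abnormal laboratory finding").

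**The concern.** The restriction has two routes to AE status: seriousness, or being the reason for stopping IMP. In a study with continuous dosing, both stay open for as long as the subject is treated. Here the only dose that can be discontinued after treatment has begun is the Period 2 dose. Once that has been given, the second route is closed, although AE collection continues to the Follow-up Visit.

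Whether a given finding is an AE then depends on the period in which it occurs and not on the finding itself. AEs are one of the outcome measures for the secondary objective of comparing co-administration with tacrolimus or cyclosporin alone. Hypokalaemia, which Section 3.3.1.1 describes as a result of the pharmacological action of SZC, and QTc changes are looked for by scheduled tests, so both fall under the restriction. For ECGs, it is also unclear whether Section 6.3.1.4 or Section 6.3.4 governs.

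**Working it through.** The plan states no figure to reproduce here. The check is mainly one of logic, with an illustration of scale.

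**Step 1. Is each route open?** Take a non-serious, symptom-free finding at a Section 5.7 level.

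| | After Period 1 dose | After Period 2 dose |
|---|---|---|
| Doses still to be given | 1 | 0 |
| SAE route (6.3.1.2) | open, but not met by a non-serious finding | open, but not met by a non-serious finding |
| Discontinuation route (6.3.1.4 with 5.7) | open and met | closed |
| Sign or symptom route (6.3.1.4) | not met, symptom-free | not met, symptom-free |
| AE under 6.3.1.4? | yes | no |

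If the finding is serious, or has symptoms, the two columns agree. They also agree for potential Hy's Law cases, which Appendix C makes SAEs.

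**Step 2. How many exposures are affected?** Section 5.1.1 plans 30 subjects per cohort and 15 per sequence. In each cohort each treatment is given to 15 subjects in Period 1 and 15 in Period 2. So 15 of 30 exposures per treatment cannot yield this type of AE. Over both cohorts, SZC is given in Period 2 to 15 (AB) + 15 (CD) = 30 of 60 subjects.

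**Step 3. What does that do to counts?** The documents give no rate, so p, the risk per dose of such a finding, is assumed. For one treatment in one cohort, the expected number of AEs is 30p if both periods count and 15p if only Period 1 counts. The chance of recording at least one is 1 − (1 − p)^n, with n = 30 or 15.

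| Assumed p | Expected, both periods | Expected, Period 1 only | P(at least one), n = 30 | P(at least one), n = 15 |
|---|---|---|---|---|
| 2% | 0.6 | 0.3 | 45.5% | 26.1% |
| 5% | 1.5 | 0.75 | 78.5% | 53.7% |
| 10% | 3.0 | 1.5 | 95.8% | 79.4% |

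This table ignores the few Period 2 doses lost to discontinuation after Period 1. Step 4 allows for them.

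**Step 4. Does it bias the comparison?** Assume true risks of 5% alone and 10% in combination. A subject with a finding in Period 1 does not get the Period 2 dose.

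- Exposures alone: 15 + 15 × (1 − 0.10) = 28.5. Recorded AEs: 15 × 0.05 = 0.75. Apparent rate: 0.75 / 28.5 = 2.6%.
- Exposures in combination: 15 + 15 × (1 − 0.05) = 29.25. Recorded AEs: 15 × 0.10 = 1.5. Apparent rate: 1.5 / 29.25 = 5.1%.
- Apparent ratio: about 1.95, against a true ratio of 0.10 / 0.05 = 2.0.

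The ratio is almost unchanged, while the absolute rates are roughly halved. With 2% and 10%, the apparent ratio is about 4.80 against a true 5.0.

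**The case against.** The strongest reply is that little is lost. Laboratory values, vital signs and ECGs are outcome measures of the same secondary objective, and Sections 10.1.2, 10.1.4, 10.1.5 and 11.2.5 tabulate them by treatment. The QTcF outlier categories include those above 500 ms and increases above 60 ms, the same cut-offs as in Section 5.7. Section 6.3.1.3 adds a sponsor review for other significant AEs. Not duplicating tabulated values as AEs is a deliberate choice. All of this stands, and it keeps the point small. It does not explain why the choice should differ by period. Section 6.3.1.4 collects intensity, causality, action taken and outcome for each AE, and a tabulated value carries none of these.

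Section 5.7 also ends by requiring the AE form. That sentence follows a list of reasons for discontinuing IMP, so it does not clearly reach a finding after the last dose. The SAE criterion for important medical events could capture some cases in either period, but only those judged serious.

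Readers might infer four stronger points that the documents do not support:

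- *That Period 2 findings escape the stopping rule.* Section 5.8 counts serious reactions and severe non-serious ones, and Section 6.3.1.4 defines severe as incapacitating. A symptom-free finding would hardly count in either period.
- *That clinically significant changes below the listed thresholds are never AEs.* Section 5.7 introduces its list as non-exhaustive, so another change that stops dosing after Period 1 is an AE. Section 6.3.4 may also bring in ECG findings.
- *That the comparison of treatments is biased.* The 1:1 sequences spread the loss almost evenly.
- *That the general definition in Section 6.3.1.1 contradicts the restriction.* It is a general definition, and Section 6.3.1.4 is the specific recording rule.

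The relation between Sections 6.3.1.4 and 6.3.4 is less clear. The closing words of the ECG sentence can be read as deferring to the restriction, but they do not say so.

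**Conclusion.** The point holds in a narrow form. For findings that are non-serious, without symptoms and at a level that would stop IMP, AE status under Section 6.3.1.4 depends on whether a dose remains. Half of the planned exposures per treatment, 15 of 30 in each cohort, cannot produce such an AE. Counts of this type are understated by about half and about equally for both treatments, and the investigator's assessment is not collected for the Period 2 cases.

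This rests on the planned 15 subjects per sequence, similar risk in both periods, and a literal reading of the restriction. The number of events concerned is unknown. Section 3.3.1.1 reports no hypokalaemia in three earlier healthy-volunteer studies of SZC, so it may be very small. Separately, the protocol does not settle whether a clinically significant ECG finding is an AE. Priority is minor.

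**What to change.** In Section 6.3.1.4, make AE status independent of a remaining dose. For example: a deterioration in a protocol-mandated assessment is reported as an AE if it fulfils any SAE criterion, or meets a discontinuation criterion already listed in Section 5.7, whether or not a further IMP dose remains. Then reconcile Sections 6.3.1.4 and 6.3.4, so that one of them states whether clinically significant ECG findings are AEs.

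This changes recording only. No threshold, dose or procedure is altered. The cost is one sentence, a cross-reference and a few more AE entries. Making every change that the investigator judges significant an AE would go further than the problem requires; that is a preference and is not needed here.
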